12.0 ROLE AND RESPONSIBILITIES

Each investigational center will identify appropriate personnel to perform all study tasks.

12.1 INVESTIGATOR

- This clinician will have responsibility to treat all subjects.
- Documents all reportable adverse events that occur during the study.
- Be responsible for signing the CRFs.
- Be responsible for providing medical care to subjects during the study.
- Have responsibility for determining eligibility.
- Conduct baseline assessments of the subject's GERD.
- Interview subjects about their GERD symptoms.
- Be available for each subject follow-up visit.

12.2 STUDY COORDINATOR

In addition to the Investigator, a Study Coordinator will be identified at each investigational center to facilitate and manage the study.

13.0 STUDY CENTER DOCUMENTATION

A study center site will provide the following documentation to Torax Medical prior to a site being activated to enroll patients:

- Study training/initiation completed for the Investigators and study staff listed on the delegation log
- Signed clinical trial agreement (CTA)
- Current signed curriculum vitae and medical licenses for all Investigators listed on the CTA

- Financial disclosure for all Investigators listed on the CTA
- IRB approval letter and approved ICF

14.0 STUDY PATIENT RECRUITMENT AND RETENTION PLAN

As needed, the Sponsor will provide study centers with materials and financial support to recruit patients for the study. All recruitment activities will require prior approval by the IRB before implementation.

Efforts will be made to ensure the retention and compliance of study patients once enrolled. Examples of strategies for subject retention include:

- Instruct study centers to obtain multiple contact numbers and addresses from a subject to make it easier to reach the participant.
- Counsel patients about the importance of returning to follow-up during informed consent and follow-up visits.
- Accommodate a subject's schedule as much as possible to make the follow-up as convenient as possible.
- Encourage the study centers to continue open communication with enrolled subjects and to schedule follow-up visits early in the protocol-defined window.
- Provide database-generated follow-up schedules to study centers and discuss dates of upcoming visits.
- Monitor follow-up rates closely so that follow-up problems can be identified and addressed as soon as possible.
- Request that study centers thoroughly document all attempts to contact enrolled subjects.

15.0 DATA HANDLING AND RECORD KEEPING

15.1 CONFIDENTIALITY

Information about study subjects will be kept confidential and managed according to applicable laws, regulations and guidelines. All subject information documented on CRFs will be referenced by a subject's identification (ID) number and initials only. If supplemental laboratory or imaging reports are submitted into the study, the subject's name or other prohibited identifiers must be deleted and the subject initials and ID number added to each item. A subject's privacy and personal health information will be protected as required by law.

15.2 SOURCE DOCUMENTS

Source data is all information, original records of clinical findings, observations, or other activities in a clinical trial necessary for the reconstruction and evaluation of the trial. Source data are contained in source documents. Examples of these original documents, and data records include: hospital records, clinical and office charts, laboratory notes, surgical notes, memoranda, subjects' diaries, questionnaires or evaluation checklists, pharmacy dispensing records, recorded data from automated instruments, copies or transcriptions certified after verification as being accurate and complete, microfiches, photographic negatives, microfilm or magnetic media, X-rays, subject files, and records kept at the pharmacy and at the laboratories involved in the clinical trial.

15.3 CASE REPORT FORMS

The study case report form (CRF) is the primary data collection instrument for the study (**Appendix D**). All data requested on the CRF must be recorded. All missing data must be explained. If a space on the CRF is left blank because the procedure was not done or the question was not asked, write "N/D". If the item is not applicable to the individual case, write "N/A". All entries should be printed legibly in ink. If any entry error has been made, to correct such an error, draw a single straight line through the incorrect entry and enter the correct data above it. All such changes must be initialed and dated. **DO NOT ERASE OR WHITE-OUT ERRORS.** For clarification of illegible or uncertain entries, print the clarification above the item, then initial and date it.

15.4 RECORDS RETENTION

The Investigator/institution will retain the study-related essential documents until two years after the final data analysis is complete.

16.0 QUALITY ASSURANCE AND QUALITY CONTROL

The Principal Investigator at each study site is responsible for assuring that accurate and complete data are collected and sent to the Sponsor. Data will be reviewed periodically by the Sponsor for missing data points, incomplete information, and discrepancies. When necessary, issues will be resolved by electronic mail, telephone, facsimile, or site visit. The Investigator will permit study-related monitoring, audits, and inspections by the IRB, the Sponsor, government regulatory bodies, and institutional compliance and quality assurance groups of all study related documents (e.g. source documents, regulatory documents, data collection instruments, study data etc.). The Investigator will ensure the capability for inspections of applicable study-related facilities (e.g. pharmacy, diagnostic laboratory, etc.).

17.0 PUBLICATION PLAN

Neither the complete nor any part of the results of the study carried out under this protocol, nor any of the information provided by the Sponsor for the purposes of performing the study, will be published or passed on to any third party without the written consent of Torax Medical. Any Investigator involved with this study is obligated to provide the Sponsor with complete test results and all data derived from the study.

	8.11 Assessment of Site Homogeneity.....	10
9	Data Monitoring Committee (DMC)	10
	Appendix: Table Shells and List of Listings to be Generated	11

1 Introduction

This is the Statistical Analysis Plan (SAP) for the final analysis of data collected under Protocol 4600 Rev 5. This SAP describes in detail the statistical methodology and statistical analyses for this protocol.

1.1 Study Objectives

The purpose of this study is to evaluate the safety and efficacy of LINX for its approved indication in subjects who have had prior gastric surgery, specifically, Laparoscopic Sleeve Gastrectomy (LSG). The objective of the study is to confirm safety and efficacy after LSG is similar to the outcomes that formed the basis for Premarket Approval (PMA) in order to support modification of the current labeling with a statement that prior gastric surgery with LSG has been evaluated for safety and efficacy.

1.2 Study Design

This is an observational, multicenter, single-arm study with prospective enrollment. Based on the observational status of the study, no formal statistical hypothesis tests will be conducted. Up to 30 subjects meeting the eligibility requirements will be implanted with LINX and followed through 12-months after implant. Up to twelve clinical sites will enroll subjects. Safety evaluations will be ongoing throughout the duration of the study, starting at the implant procedure. Efficacy endpoints will be evaluated at the 12-month visit.

Safety will be assessed by evaluating device and/or procedure related adverse events, perioperative complications, device malfunctions, device removals, and hospital readmissions experienced by subjects post-LINX implant out to 12 months. Esophageal anatomy and functionality will be monitored by performing manometry and barium esophagram at 12-months post-implant. This will allow for identification of any abnormal or atypical findings. Further, device migration will be assessed by confirming device position at the gastroesophageal junction (GEJ) by obtaining upright, bi-plane X-rays and device erosion will be assessed by performing endoscopy at the 12-month visit.

Efficacy will be assessed by evaluating the percentage of subjects reporting at the 12-month follow-up:

- Normalization of total distal acid exposure time or at least 50% reduction in total distal acid exposure time compared to baseline.
- >50% reduction in total GERD-HRQL score compared to baseline (off PPIs).
- >50% reduction in average daily PPI dosage compared to baseline.

2 Treatment Assignment

This is a prospective, multicenter, single-arm, observational study, where subjects serve as their own control.

3 Randomization and Blinding Procedures

This is an observational, single-arm study. No randomization will occur, and no blinding procedures will be needed.

4 Interval Windows

Interval windows are not defined for the purpose of analysis in this study outside of the visit windows that are provided in the Study Schedule and Assessments in the final protocol. There will be no assigning of observations to time points outside of the visit to which they are recorded in the electronic Case Report Forms (eCRFs). Data collected in Unscheduled Visits forms will be listed as such. Observations collected outside of the 12-month protocol-specified visit window may be still be included in the analysis of primary effectiveness and safety endpoints since the device under study is an implant and longer term follow-up (i.e. beyond 12-months) is still considered informative towards evaluating the overall benefit-risk profile of the device in subjects with prior LSG surgery.

5 Levels of Significance

No formal statistical hypotheses are specified for this study. For continuous efficacy parameters, the p-value for a one sample, paired t-test to test if there is statistical evidence that the change from baseline is not equal to zero will be given. All estimation of endpoints will be performed using 95% confidence intervals.

6 Analysis Sets

All subjects who meet the eligibility criteria, provide informed consent, complete baseline assessments and undergo the LINX procedure will represent the study population for analysis. This set of subjects will be labeled as Full Analysis Set (FAS). This set of subjects will be identified by having answered “Yes” to the question “Was the LINX device implanted?” on the Implant Data eCRF.

7 Sample Size Justification

No formal sample size calculation has been performed for this study. The sample size planned for the study is up to 30 eligible subjects recruited from 12 clinical sites and no site will enroll more than 6 subjects without prior written approval provided by the Sponsor. No formal hypothesis has been tested in this study; thus, the sample size is not statistically sized, but rather is considered

sufficient for a descriptive summary of LINX performance for subjects who have had prior gastric surgery with LSG through confidence interval estimation and evaluation of safety and efficacy.

8 Analyses to be Conducted

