Appendix C: Informed Consent (Template)

Appendix D: Case Report Forms (CRFs)

Protocol Synopsis**Protocol ID 4600**

Sponsor	Torax Medical, Inc. [name] [contact] [contact]
Study Title	RELIEF Study: A Prospective, Multicenter Study of Reflux Management with the LINX® System for Gastroesophageal Reflux Disease after Laparoscopic Sleeve Gastrectomy
Study Device	The LINX® Reflux Management System (LINX)
Indication	The LINX® Reflux Management System is a laparoscopic, fundic-sparing anti-reflux procedure indicated for patients diagnosed with Gastroesophageal Reflux Disease (GERD) as defined by abnormal pH testing, and who are seeking an alternative to continuous acid suppression therapy (i.e. proton pump inhibitors or equivalent) in the management of their GERD.
FDA Approval	March 22, 2012
Study Design	An observational, multicenter, single-arm study with prospective enrollment.
Purpose	To evaluate the safety and efficacy of LINX for its approved indication in patients who have had prior gastric surgery, specifically, laparoscopic sleeve gastrectomy (LSG).
Objective	To confirm safety and efficacy after LSG in patients indicated for LINX is similar to the outcomes that formed the basis for Premarket Approval (PMA) to support modification of the current labeling with a statement that prior gastric surgery with LSG has been evaluated for safety and efficacy.
Number of Subjects	Up to 30 subjects
Study Centers	Up to 12 implanting sites in the U.S.
Study Duration	36 months (24-month enrollment period + 12-month follow-up period)
Evaluation of Safety	Rate of serious device and procedure related adverse events assessed by reporting all adverse events and by estimating the rate of serious device and procedure related adverse events through 12 months post implantation. Safety will also be evaluated by endoscopy to assess the mucosa and abdominal/chest X-ray evaluations to verify device location at 12 months post implantation.
Evaluation of Efficacy	Percentage of subjects reporting at the 12-month follow-up: 
• Normalization of total distal acid exposure (% total time pH<4) or at least 50% reduction in total distal acid exposure compared to baseline• At least 50% reduction in total GERD-HRQL score compared to baseline (off PPIs)• At least 50% reduction in average daily PPI dosage compared to baseline
Study Management	Torax Medical Inc. or Designate

Schedule of Data Collection

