8.5.1 Esophageal Acid Exposure

Testing will be performed with subjects off PPIs. The subject's total distal esophageal acid exposure time at baseline will serve as the control and will be compared to results at the 12-month visit. Normalization for total distal ambulatory esophageal pH testing is defined as pH < 4 for < 4.5% of the time. If longer pH evaluations are received, the total distal acid exposure time will be recorded as a 24-hour average (e.g. 48-hour Bravo testing).

The proportion of subjects achieving pH normalization or at least a >50% reduction from baseline to the result at the 12-months will be summarized descriptively for the FAS. Two-sided 95% CI will also be constructed using exact Clopper-Pearson method.

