8.5.3 Use of PPIs

Subject's average daily dose of PPI will be evaluated. The subject's baseline average daily dosage will serve as the control and be compared to the subject's average daily dosage 12 months post-procedure.

The proportion of subjects with at least 50% reduction in daily PPI use from baseline at 12 months will be reported. In addition, a two-sided 95% CI will be provided for the proportion of success (>=50% reduction achieved).

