Median (Min, Max)	xx.x (xx, xx)	xx.x (xx, xx)

Denominator and percentages are based on subjects with non-missing data.

Table 6
 Bravo pH Normalization or $\geq 50\%$ Reduction Compared to Baseline (Off PPI)
 Full Analysis Set

Parameter	Baseline	12 Months Follow-Up	Change from Baseline to 12 Months Follow-Up	% Successful at 12 Months Follow-Up [1]
Total % Time				
n	xx	xx	xx	
Mean (SD)	xx.x (xx.x)	xx.x (xx.x)	xx.x (xx.x)	
Median (Min, Max)	xx.x (xx, xx)	xx.x (xx, xx)	xx.x (xx, xx)	
95% Confidence Interval			(xx.xxx, xx.xxx)	
p-value[2]			0.xxx	
Number of Subjects were Successful				xx (xx.x%)
Number of subjects with pH normalization ($\leq 4.5\%$)				xx (xx.x%)
Number of subjects with $\geq 50\%$ reduction in total distal acid exposure				xx (xx.x%)

Denominator and percentages are based on subjects completed baseline and 12 months follow-up.

[1] % Successful is defined as number of subjects meeting the success criterion of pH normalization or at least 50% reduction in total distal acid exposure.

[2] From one-sample, paired t test against the change from baseline is equal to zero.

Table 7
Summary of DeMeester Score Components
Full Analysis Set

Parameter	Baseline	12 Months Follow-Up	Change from Baseline to 12 Months Follow-Up
Daily Average of Total % Time			
n	xx	xx	xx
Mean (SD)	xx.x (xx.x)	xx.x (xx.x)	xx.x (xx.x)
Median (Min, Max)	xx.x (xx, xx)	xx.x (xx, xx)	xx.x (xx, xx)
Daily Average of Upright % Time			
n	xx	xx	xx
Mean (SD)	xx.x (xx.x)	xx.x (xx.x)	xx.x (xx.x)
Median (Min, Max)	xx.x (xx, xx)	xx.x (xx, xx)	xx.x (xx, xx)
Daily Average of Supine % Time			
n	xx	xx	xx
Mean (SD)	xx.x (xx.x)	xx.x (xx.x)	xx.x (xx.x)
Median (Min, Max)	xx.x (xx, xx)	xx.x (xx, xx)	xx.x (xx, xx)
Daily Average of Number of Reflux Episodes (pH <4)			
n	xx	xx	xx
Mean (SD)	xx.x (xx.x)	xx.x (xx.x)	xx.x (xx.x)
Median (Min, Max)	xx.x (xx, xx)	xx.x (xx, xx)	xx.x (xx, xx)
Daily Average of Number of Reflux Episodes > 5 mins			
n	xx	xx	xx
Mean (SD)	xx.x (xx.x)	xx.x (xx.x)	xx.x (xx.x)
Median (Min, Max)	xx.x (xx, xx)	xx.x (xx, xx)	xx.x (xx, xx)
Daily Average of Longest Reflux Episode (min)			
n	xx	xx	xx
Mean (SD)	xx.x (xx.x)	xx.x (xx.x)	xx.x (xx.x)
Median (Min, Max)	xx.x (xx, xx)	xx.x (xx, xx)	xx.x (xx, xx)

Note: For all parameters, the within subject average of the values within a visit is first calculated prior to summarizing across all subjects at the given visit.

Table 7
 Summary of DeMeester Score Components
 Full Analysis Set

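### The SAP states its efficacy success rules inconsistently: Table 6 counts exactly 4.5% acid exposure as normal, and SAP 1.2 and 8.5.1 use a strict 50% sign where the protocol says at least 50%

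*SAP*

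**What the plan says.** There are three responder endpoints at 12 months.

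- **Acid exposure, normalization.** SAP 8.5.1 has normalization "defined as pH < 4 for < 4.5% of the time", and protocol 10.1.1 says the same. Inclusion criterion 6 admits subjects at 4.5% or more. In the Table 6 shell, the row "Number of subjects with pH normalization" carries the limit ≤4.5%.
- **Acid exposure, reduction.** SAP 8.5.1 asks for "at least a >50% reduction from baseline". Protocol 5.2, SAP 1.2 and Table 6 use at least 50%.
- **GERD-HRQL.** SAP 1.2 lists ">50% reduction in total GERD-HRQL score compared to baseline (off PPIs" (closing bracket omitted). The protocol synopsis, protocol 5.2 and SAP Table 14 use at least 50%. SAP 8.5.2, the section on this endpoint, gives no responder threshold.
- **PPI dose.** SAP 1.2 lists ">50% reduction in average daily PPI dosage compared to baseline". The protocol synopsis has "At least 50% reduction in average daily PPI dosage compared to baseline", and protocol 5.2 uses ≥50%. SAP 8.5.3 attaches its confidence interval to the "proportion of success (>=50% reduction achieved" (closing bracket omitted), and Table 15 also uses at least 50%.

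The title of Table 6 begins "Bravo pH Normalization", while Table 5 lists trans-nasal and impedance catheter tests beside the Bravo capsule.

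**The concern.** A responder rate needs one rule for the subject who lands on the boundary. Here two boundaries are drawn twice.

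At 4.5% the table contradicts the definition it is meant to implement, and a value that qualifies a subject as abnormal at entry would count as normal at 12 months. At 50%, an exact halving fails the strict rule and passes the inclusive one. Such a value is possible: PPI dose moves in steps, so two equal daily doses cut to one is exactly half, and GERD-HRQL is built from whole-number items.

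The responder proportions are meant to support a labeling statement (SAP 1.1) from at most 30 subjects. SAP 8.9 summarizes observed data only, and SAP 8.8 reports lower follow-up than anticipated, so one subject carries visible weight. SAP 8.1 requires departures from the plan to be identified in the final output. With two rules in the same plan, either choice departs from some line of it.

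**Working it through.** The documents give no expected responder rate and no sample size calculation, so there is no planned figure to reproduce. The check sets the rules side by side, finds which subjects they classify differently, and sizes the effect per subject.

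**1. Rules side by side**

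| Endpoint | Protocol | SAP 1.2 | SAP section 8.5 | SAP shell |
|---|---|---|---|---|
| Normalization | <4.5% (10.1.1) | no limit given | <4.5% (8.5.1) | ≤4.5% (Table 6) |
| Acid exposure reduction | at least 50% | at least 50% | at least, combined with >50% (8.5.1) | at least 50% (Table 6) |
| GERD-HRQL reduction | at least 50% | >50% | none (8.5.2) | at least 50% (Table 14) |
| PPI dose reduction | at least 50% | >50% | ≥50% (8.5.3) | at least 50% (Table 15) |

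**2. The 4.5% limit.** Let B be baseline and F the 12-month value. The two limits differ only at F = 4.5%. The reduction is then

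r = (B − 4.5)/B = 1 − 4.5/B,

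and r ≥ 0.50 exactly when B ≥ 9.0%. Inclusion criterion 6 requires B ≥ 4.5%. With the at-least-50% rule, composite success therefore differs only when F = 4.5% and 4.5% ≤ B < 9.0%:

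- B = 4.5%: r = 0. Table 6 scores success with no change from baseline; SAP 8.5.1 scores failure.
- B = 8.0%: r = 3.5/8.0 = 43.75%. Table 6 success; SAP 8.5.1 failure.
- B = 10.0%: r = 5.5/10.0 = 55%. Success either way.

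The separate normalization row in Table 6 would change for any F of exactly 4.5%, whatever the baseline.

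**3. The 50% limit.** An exact halving gives r = (B − B/2)/B = 0.50, which fails >0.50 and passes ≥0.50.

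- *PPI:* the strict sign stands only in SAP 1.2. SAP 8.5.3 and Table 15 would count the halving as success.
- *GERD-HRQL:* SAP 8.5.2 has ten items scored 0 to 5 and calls the overall score their average. Percent reduction is the same for a sum S or an average: 1 − (S12/10)/(S0/10) = 1 − S12/S0. With all ten items answered, S is an integer from 0 to 50, and any even baseline can be halved exactly.
- *Acid exposure:* a halving affects the composite only if F is not already normal. With F = B/2 ≥ 4.5%, that means B ≥ 9.0%.

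**4. Size.** One boundary subject moves a rate by 1/n: 1/30 = 3.3 points, and 1/20 = 5.0 points at an assumed reduced denominator.

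As an illustration only, assume 80% responders under ≥50%, of whom k halved exactly. Intervals are Clopper-Pearson 95%, the method SAP 8.5.1 names for acid exposure.

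| n | k | Rate under >50% | 95% CI |
|---|---|---|---|
| 30 | 0 | 24/30 = 80.0% | 61.4 to 92.3 |
| 30 | 1 | 23/30 = 76.7% | 57.7 to 90.1 |
| 30 | 3 | 21/30 = 70.0% | 50.6 to 85.3 |
| 20 | 0 | 16/20 = 80.0% | 56.3 to 94.3 |
| 20 | 1 | 15/20 = 75.0% | 50.9 to 91.3 |

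The row with k = 0 is also the rate under ≥50%. The documents give neither the 80% nor any value of k.

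**The case against.** **The operative text is already right.** SAP 1.2 is a design summary. Output programmed from SAP 8.5.3 and Tables 6, 14 and 15 would count an exact halving as success, as the protocol does. This stands fully for PPI, where both the analysis section and the shell agree with the protocol. It is weaker for GERD-HRQL: SAP 8.5.2 gives no threshold, so the inclusive rule rests on the Table 14 shell alone, and the SAP appendix calls the shells a guide to general layout.

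**The strict sign may be a ≥ that lost its underline.** The SAP 1.2 bullets closely follow protocol 5.2, which has ≥, and the wording in SAP 8.5.1 makes sense only with ≥. Protocol Table 4 shows a plus sign alone beside symmetric windows, so signs may have been lost elsewhere too. Against this, ≥ survives in the Table 6 title and the typed form in SAP 8.5.3. Only the source PDF can settle it. A lost sign would not readily explain Table 6, which shows ≤ where two sections say <.

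**Exact ties may be rare, and nothing is tested on these proportions.** Both points limit the weight. No performance goal is set, and a 12-month value of exactly 4.5% should be uncommon.

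**A reader might infer that the Bravo title removes catheter-tested subjects from the endpoint.** The documents do not support that. The Table 6 footnote sets its denominator by completion of baseline and 12 months, with no device limit. SAP 8.5.1 mentions Bravo only as an example, and SAP 8.1 treats a title change as minor. The title is misleading, but it is not an exclusion rule.

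**Conclusion.** The point holds as a minor inconsistency in endpoint definitions. The clearest part is Table 6, whose ≤4.5% contradicts the definition in the protocol and the SAP. It changes composite success only for a 12-month value of exactly 4.5% with a baseline below 9.0%. The second part is the strict 50% sign in SAP 1.2 and 8.5.1, subject to checking the source PDF. It matters most for GERD-HRQL and little for PPI.

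Each boundary subject is worth 3.3 points at n = 30 or 5 points at an assumed n = 20, on a descriptive proportion and its interval.

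A reader might infer that exact halving of PPI dose is common and that the PPI success rate could therefore shift by ten points or more. The documents do not support this. They give no dose distribution and no count of halvers, and the passages that produce the PPI result do not use the strict rule. Nor does any formal conclusion turn on these rules, because the plan sets no hypothesis or success threshold.

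**What to change.** - Check the > signs in SAP 1.2 and 8.5.1 against the source PDF. Where they are strict, replace them with ≥50% for GERD-HRQL and PPI in 1.2 and for acid exposure in 8.5.1, to match the protocol.
- Change the normalization row of Table 6 to <4.5%.
- Remove Bravo from the Table 6 title, so that it clearly covers every pH method in Table 5.

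These edits restore the protocol's own definitions and add no new rule. The cost is a few words in the SAP text and one shell, with no effect on data collection. SAP 8.1 allows the title change without an amendment. The two definition changes are better recorded in a SAP revision before the final analysis is run.
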